9.2 Serious adverse event reporting

9.2.1 Definition of SAE

An SAE is defined as any adverse event (appearance of (or worsening of any pre-existing) undesirable sign(s), symptom(s) or medical conditions(s)) which meets any one of the following criteria:

- is fatal or life-threatening
- results in persistent or significant disability/incapacity
- constitutes a congenital anomaly/birth defect
- requires inpatient hospitalization or prolongation of existing hospitalization, unless hospitalization is for:
 - treatment on an emergency outpatient basis for an event not fulfilling any of the definitions of a SAE given above and not resulting in hospital admission
 - social reasons and respite care in the absence of any deterioration in the subject's general condition
- is medically significant, e.g. defined as an event that jeopardizes the subject or may require medical or surgical intervention.

All malignant neoplasms will be assessed as serious under "medically significant" if other seriousness criteria are not met.

Life-threatening in the context of a SAE refers to a reaction in which the subject was at risk of death at the time of the reaction; it does not refer to a reaction that hypothetically might have caused death if it were more severe (see Annex IV, ICH-E2D Guideline).

[figure not shown]
Medical and scientific judgment should be exercised in deciding whether other situations should be considered serious reactions, such as important medical events that might not be immediately life threatening or result in death or hospitalization but might jeopardize the subject or might require intervention to prevent one of the other outcomes listed above. Examples of such events are intensive treatment in an emergency room or at home for allergic bronchospasm, blood dyscrasias or convulsions that do not result in hospitalization or development of dependency or abuse (see Annex IV, ICH-E2D Guideline).

Any suspected transmission via a medicinal product of an infectious agent is also considered a serious adverse reaction.

All AEs (serious and non-serious) are captured on the CRF; SAEs also require individual reporting to Novartis Drug Safety & Epidemiology (DS&E) as per [Section 9.2.2](#).

9.2.2 SAE reporting

To ensure subject safety, every SAE, regardless of causality, occurring after the subject has provided informed consent and until 30 days [after the last study visit/ following the last administration of study treatment if there are post-treatment follow-up visits with no required procedures] must be reported to Novartis **within 24 hours of learning of its occurrence** as described below. Any SAEs experienced after this period should only be reported to Novartis if the investigator suspects a causal relationship to study treatment.

Note: SAEs reported by subjects deemed to be screen failures must be reported to Novartis as outlined here with appropriate information also captured in the CRFs as specified in the Site Operations Manual.

All follow-up information for the SAE including information on complications, progression of the initial SAE and recurrent episodes must be reported as follow-up to the original episode within 24 hours of the investigator receiving the follow-up information. An SAE occurring at a different time interval or otherwise considered completely unrelated to a previously reported one must be reported separately as a new event.

Follow-up information provided must describe whether the event has resolved or continues, if and how it was treated, whether the blind was broken or not (if applicable) and whether the subject continued or withdrew from study participation. Each re-occurrence, complication, or progression of the original event must be reported as a follow-up to that event regardless of when it occurs.

If the SAE is not previously documented in the Investigator's Brochure or Package Insert (new occurrence) and is thought to be related to the study treatment a Drug Safety and Epidemiology Department associate may urgently require further information from the investigator for Health Authority reporting. Novartis may need to issue an Investigator Notification (IN) to inform all investigators involved in any study with the same study treatment that this SAE has been reported. Suspected Unexpected Serious Adverse Reactions (SUSARs) will be collected and reported to the competent authorities and relevant ethics committees in accordance with EU Guidance 2011/C 172/01 or as per national regulatory requirements in participating countries.

Follow the detailed instructions outlined in the Site Operations Manual regarding the submission process for reporting SAEs to Novartis. Note: **SAEs must be reported to Novartis within 24 hours** of the investigator learning of its occurrence/receiving follow-up information.

9.3 Liver safety monitoring

To ensure subject safety and enhance reliability in determining the hepatotoxic potential of an investigational drug, a standardized process for identification, monitoring and evaluation of liver events has to be followed.

[figure not shown]
Please refer to [Table 15-1-Appendix 1](#) for complete definitions of liver events.

Follow-up of liver events

Every liver event defined in [Table 15-1-Appendix 1](#) should be followed up by the investigator or designated personnel at the trial site, as summarized below. Additional details on actions required in case of liver events are outlined in [Table 15-2-Appendix 1](#).

- Repeating liver chemistry tests (ALT, AST, TBL, PT/INR, ALP and γ GT) to confirm elevation within 48-72 hours.

These liver chemistry repeats should be performed using the local laboratory used by the site. Repeat laboratory test results must be reported as appropriate via an electronic data transfer (if applicable), or entered on the appropriate unscheduled local laboratory CRF.

- If the initial elevation is confirmed, close observation of the subject will be initiated, including consideration of treatment interruption if deemed appropriate.
- Discontinuation of the investigational drug (refer to [Section 7.2](#) (Discontinuation of study treatment), if appropriate
- Hospitalization of the subject if appropriate
- Causality assessment of the liver event
- Thorough follow-up of the liver event should include:
 - Repeating liver chemistry tests two or three times weekly. Testing should include ALT, AST, ALP, PT/INR, and gGT. If total bilirubin is elevated $> 2 \times$ ULN, fractionation into direct and indirect bilirubin is required. To rule out muscular origin of transaminase elevations, CPK should be measured along with liver chemistry tests. Frequency of retesting can decrease to once a week or less if abnormalities stabilize or the study drug has been discontinued and the subject is asymptomatic. Retesting should be continued up to resolution.
 - Obtaining a more detailed history of symptoms and prior or concurrent diseases.
 - Obtaining a history of concomitant drug use (including nonprescription medications and herbal and dietary supplement preparations), alcohol use, recreational drug use, and special diets.
 - Exclusion of underlying liver disease, as specified in [Table 15-3](#).
 - Imaging such as abdominal US, CT or MRI, as appropriate
 - Obtaining a history of exposure to environmental chemical agents.
 - Considering gastroenterology or hepatology consultations.

[figure not shown]
All follow-up information, and the procedures performed must be recorded as appropriate in the CRF.

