7.2 Discontinuation of study treatment

Discontinuation of study treatment for a subject occurs when study treatment is stopped earlier than the protocol planned duration. Discontinuation of study treatment can be decided by either the subject or the investigator.

Study treatment must be discontinued under the following circumstances:

[figure not shown]
- Subject decision - subjects may choose to discontinue study treatment for any reason at any time.
- The investigator believes that continuation would negatively impact the safety of the subject or the risk/benefit ratio of trial participation.
- Any protocol deviation that results in a significant risk to the subject's safety.
- Pregnancy
- Use of prohibited treatments.

Study treatment of individual subject will be discontinued when that subject experiences:

- Clinically significant diarrhea, suspected to be related to the study drug, that may put the subject at risk at the discretion of the investigator and in consultation with the sponsor
- Clinically significant symptomatic orthostasis confirmed by repeated orthostatic blood pressure changes (more than a 20 mmHg drop in systolic or 10 mmHg drop in diastolic blood pressure and increase in heart rate >20 bpm (compared to the sitting results) when blood pressure and pulse are taken after at least 3 minutes standing)
- Clinically significant urinary tract or genitourinary infections, at the discretion of the investigator and in consultation with the sponsor if deemed necessary.
- Clinically symptomatic hypoglycemia confirmed by repeated blood glucose levels (<56 mg/dL).
- Ketoacidosis (symptoms of ketoacidosis include nausea, vomiting, abdominal pain, unusual tiredness and trouble breathing) confirmed by blood pH and ketones bodies in both plasma and urine.
- Any laboratory abnormalities that in the judgment of the investigator, taking into consideration the subject's overall status, prevents the subject from continuing participation in the study.
- Any hospitalization, or other SAE, that is suspected to be related to the study treatment.

If discontinuation of study treatment occurs, the investigator must determine the primary reason for the subject's premature discontinuation of study treatment and record this information on the Dosage Administration CRF.

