ALT or AST elevation with coagulopathy	
ALT or AST $> 3 \times$ ULN and INR > 1.5 (in the absence of anticoagulation)
ALT or AST elevation accompanied by symptoms	
ALT or AST $> 3 \times$ ULN accompanied by (general) malaise, fatigue, abdominal pain, nausea, or vomiting, or rash, or eosinophilia
Isolated ALT or AST elevation	
ALT or AST $> 8 \times$ ULN$5 \times$ ULN $<$ ALT/AST $\leq 8 \times$ ULN$3 \times$ ULN $<$ ALT/AST $\leq 5 \times$ ULN
Isolated ALP elevation	
ALP $> 2 \times$ ULN (in the absence of known bone pathology)
Others	
Any clinical event of jaundice (or equivalent term)Any adverse event potentially indicative of liver toxicity

Table 15-2 Actions required for Liver Events

Criteria	Actions required
Potential Hy's Law case	
ALT or AST elevation with coagulopathy	
 • Discontinue the study treatment immediately
ALT or AST elevation accompanied by symptoms	
 • Hospitalize, if clinically appropriate • Establish causality
Isolated ALT or AST elevation $> 8 \times \text{ULN}$	
 • Complete CRFs per liver event guidance
Jaundice	
Isolated ALT or AST elevation > 5 to $\leq 8 \times \text{ULN}$	
 • If confirmed, consider interruption or discontinuation of study drug • If elevation persists for more than 2 weeks, discontinue the study drug • Establish causality • Complete CRFs per liver event guidance
Isolated ALT or AST elevation > 3 to $\leq 5 \times \text{ULN}$ (patient is asymptomatic)	
 • Monitor liver chemistry tests two or three times weekly
Isolated ALP elevation	
 • Repeat liver chemistry tests within 48-72 hours • If elevation is confirmed, measure fractionated ALP; if $>50\%$ is of liver origin, establish hepatic causality • Complete CRFs per liver event guidance
Any AE potentially indicative of liver toxicity	
 • Consider study treatment interruption or discontinuation • Hospitalize if clinically appropriate • Complete CRFs per liver event guidance

Table 15-3 Exclusion of underlying liver disease

Disease	Assessment

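### For the most serious liver events, Section 9.3 read with 7.2 gives a softer stopping instruction than Table 15-2, and Section 6.5 bars the interruption that 9.3 and the table both offer

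*Protocol*

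**What the plan says.** Four places in the protocol bear on stopping or interrupting LIK066 after a liver signal. The SAP is silent.

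- **Section 9.3 (liver safety monitoring).** The follow-up list applies to "Every liver event defined in" Table 15-1, so it includes the top tier. It begins with repeat chemistry "to confirm elevation within 48-72 hours". The next item reads "If the initial elevation is confirmed, close observation of the subject will be initiated, including consideration of treatment interruption if deemed appropriate". A separate item, "Discontinuation of the investigational drug (refer to" Section 7.2), is qualified as applying where appropriate. The section also describes its list as a summary and adds: "Additional details on actions required in case of liver events are outlined in" Table 15-2.
- **Table 15-2 (Appendix 1).** For the top tier the action is "Discontinue the study treatment immediately", with no confirmation step. For isolated ALT or AST above 5 and up to 8 x ULN it is "If confirmed, consider interruption or discontinuation of study drug".
- **Section 7.2 (discontinuation of study treatment).** The list names orthostasis, hypoglycemia, ketoacidosis, infections and clinically significant diarrhea, but no liver event, and it does not cite Table 15-2. Laboratory findings come in through the item that begins "Any laboratory abnormalities that in the judgment of the investigator". Two other items could also catch a liver case: the investigator's view that continuing would harm the subject, and a hospitalization or other SAE suspected to be related to treatment.
- **Section 6.5.** Dose adjustments and interruptions are ruled out.

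**The concern.** A stopping rule should give the same answer whichever section the site opens. Here a reader of 9.3 is told to repeat the test, observe, consider interruption, and discontinue under 7.2 where appropriate. A reader of Table 15-2 is told to stop at once. A reader of 6.5 learns that interruption is not available at all.

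The design gives the difference practical weight. Dosing comes in three 3-day blocks separated by drug-free washouts, so the decision after one block settles whether the subject is exposed again in the next. Section 3.6 lists hepatic toxicity among the possible risks of LIK066, and 9.3 says its aim is a standardized process for liver events. The main issue is subject safety. A secondary issue is that the rule a site follows decides whether that subject contributes later periods to the crossover comparison.

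**Working it through.** The plan states no figure to reproduce here. The check is a comparison of text plus day arithmetic.

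**Step 1. Instructions by tier**

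| Liver event | Section 9.3 with 7.2 | Table 15-2 | Match? |
|---|---|---|---|
| Potential Hy's law; ALT/AST elevation with coagulopathy; ALT/AST elevation with symptoms; isolated ALT/AST > 8 x ULN; jaundice | Repeat in 48-72 h; if confirmed, consider interruption; discontinue under 7.2 where appropriate | Immediate discontinuation, no confirmation step | No |
| Isolated ALT/AST > 5 to <= 8 x ULN | Same | Confirm, then consider interruption or discontinuation | Yes |

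Table 15-2 is broken in the extracted text. The immediate-stop action is read as shared by the five classes in the first row, which is the natural reading of merged cells. Because the table asks for confirmation in one tier and not in the other, it treats confirmation as a distinction between tiers. The list in 9.3 does not carry that distinction.

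**Step 2. Where the cross-references lead**

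- For required actions, 9.3 leads to Table 15-2, as a source of additional detail.
- For discontinuation, 9.3 leads to 7.2, which has no liver trigger and no link back to the table.
- By contrast, the triggers monitored in 9.8 to 9.10 (hypoglycemia, orthostasis, ketoacidosis) all appear in the 7.2 list.

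**Step 3. Interruption**

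Section 6.5 does not permit it. Section 9.3 and Table 15-2 both offer it as an option. These statements cannot all stand as written.

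**Step 4. Doses at stake**

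Inputs:

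- Dosing on Days 1-3, 9-11 and 17-19 (Section 3.1).
- Scheduled on-treatment chemistry predose on Days 3, 11 and 19 (Table 8-1, as extracted).
- Repeat test 2 to 3 days later (Section 9.3).
- Assumption: the dose on the sampling day has already been given when the result is known.

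Formulas: repeat day = sample day + 2 to 3; maximum further doses = scheduled doses after the sample day.

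| Sample | Repeat falls on | Next scheduled dose | Maximum further doses |
|---|---|---|---|
| Day 3 | 3 + 2 to 3 = Day 5-6 (washout) | Day 9 | 3 + 3 = 6 |
| Day 11 | 11 + 2 to 3 = Day 13-14 (washout) | Day 17 | 3 |
| Day 19 | 19 + 2 to 3 = Day 21-22 | none | 0 |

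Re-dosing in a later period is therefore possible after two of the three scheduled samples.

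**Step 5. Sensitivity of the timing**

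Section 10.3 has laboratory samples processed centrally and gives no turnaround time. If the first result takes 0 to 3 days (an assumption), the repeat after a Day 3 sample falls between 3 + 0 + 2 = Day 5 and 3 + 3 + 3 = Day 9. At the long end it reaches the next dosing day. The maximum dose counts in Step 4 do not change.

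An event detected clinically on Day 1 or Day 9 would be repeated on Day 3-4 or Day 11-12. If a site read the 9.3 list as a sequence and waited, 1 to 2 further doses could be given in that same period.

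**The case against.** The strongest reply is that the protocol largely resolves this itself. Section 9.3 calls its list a summary for all tiers and sends the reader to Table 15-2 for the actions required, so a site that follows the link finds the immediate rule. Discontinuation where appropriate, in an all-tier summary, is compatible with a table that says when it is required. This reply stands in part. The link exists, but it is offered as additional detail, nothing says the table prevails over the list, and for discontinuation itself 9.3 names 7.2.

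A second reply is that 7.2 would catch serious cases anyway. Its item on a hospitalization or SAE suspected to be related leaves no judgment about stopping, and Section 9.2.1 counts medically significant events as SAEs. This too stands in part. The item requires suspected relatedness, whereas Table 15-2 lists establishing causality as a separate action. A symptom-free isolated ALT above 8 x ULN that is not reported as a related SAE would reach 7.2 only through items that rest on the investigator's judgment.

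Three stronger readings are tempting, and the documents do not support them:

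- *That there are three competing liver rules.* Section 7.2 is silent on liver events, and silence is not a third rule. The mismatch is between 9.3 and Table 15-2, and only in the top tier.
- *That 9.3 forbids stopping before confirmation.* The confirmation condition attaches to close observation and the consideration of interruption. The discontinuation item carries no such condition.
- *That an affected subject would receive six more doses.* Six is a ceiling. It requires a top-tier event on Day 3, a site that does not apply Table 15-2, no 7.2 item being triggered, and a decision to re-dose in both later periods.

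**Conclusion.** The inconsistency is real, and it is limited to the top tier of liver events. For that tier, 9.3 read with 7.2 is softer than Table 15-2. The pointer from 9.3 to the table reduces the problem without removing it, and 7.2 is only a partial backstop. The conflict between 6.5 and the interruption option in 9.3 and Table 15-2 is the most direct contradiction.

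Its size is at most 6 further doses for a subject with a Day 3 result, 3 for Day 11 and 0 for Day 19. This rests on the five-row reading of Table 15-2, the extracted chemistry schedule, and a site that relies on 9.3 and 7.2 alone. Few cases are expected: Section 4.2 excludes subjects with raised liver tests at screening, and Section 1.3.1 reports no significant laboratory abnormalities related to LIK066 in completed studies. A reader might infer that the primary comparison or the power is affected through lost or retained periods. Nothing in the documents allows that to be estimated, and no such effect has been shown. The case for correction is consistency of a safety rule, and the correction is cheap.

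**What to change.** Reconcile Sections 6.5, 7.2 and 9.3 with Table 15-2 so that:

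- each liver event tier has one stated action and one statement of whether confirmation comes first;
- the protocol says which passage governs if they differ;
- the 7.2 list refers to that passage, as it already does in substance for the triggers monitored in 9.8 to 9.10;
- 6.5 and the interruption wording in 9.3 and Table 15-2 agree. Section 9.9 and Table 16-1 also use hold or interruption wording, so an edit to 6.5 should be checked against them.

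Which rule applies to each tier is a clinical decision for the sponsor's safety team, and none is proposed here. The cost is protocol wording and cross-references in an amendment, with no added tests or visits and no change to the SAP.

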9.4 Renal safety monitoring

Renal events are defined as one of the following:

- Confirmed (after ≥ 24 h) increase in serum creatinine of $\geq 25\%$ compared to baseline during normal hydration status, and deemed as a new onset renal events in subjects with reduced renal function at the discretion of investigator(s)
- A doubling in the urinary albumin-creatinine ratio (ACR) or urinary protein-creatinine ratio (PCR).
- New onset ($\geq 1+$) proteinuria or hematuria

Every renal laboratory trigger or renal event must be followed up by the investigator or designated personnel at the trial site. Recommended follow-up assessments are listed in [Section 16-Appendix 2](#).

9.5 Reporting Medication errors including misuse/abuse

Medication errors are unintentional errors in the prescribing, dispensing, administration or monitoring of a medicine while under the control of a healthcare professional, patient/subject or consumer (EMA definition).

Misuse refers to situations where the medicinal product is intentionally and inappropriately used not in accordance with the protocol.

Abuse corresponds to the persistent or sporadic, intentional excessive use of a medicinal product, which is accompanied by harmful physical or psychological effects.

All study treatment errors and uses outside of what is foreseen in the protocol will be collected in the dose administration record (DAR) CRF. Study treatment errors are only to be reported to Novartis Drug Safety and Epidemiology department if the treatment error is associated with an SAE.

All instances of misuse or abuse must be documented in the adverse event (AE) CRF irrespective of the misuse/abuse being associated with an AE/SAE. In addition, all instances of misuse or abuse must be reported to Novartis Drug Safety and Epidemiology. As such, instances of misuse or abuse are also to be reported using the SAE form/CRF. [Table 9-1](#) summarizes the reporting requirements.

Table 9-1 Summary of reporting requirements for medication errors

Treatment error type	Document in Dose Administration (DAR) CRF	Document in AE CRF	Complete SAE form/CRF
Unintentional study treatment error	Yes	Only if associated with an AE	Only if associated with an SAE
Misuse/Abuse	Yes	Yes	Yes, even if not associated with a SAE

For more information on AE and SAE definition and reporting requirements, please see [Section 9.1](#) and [Section 9.2](#), respectively.

9.6 Pregnancy reporting

To ensure subject safety, each pregnancy occurring after signing the informed consent must be **reported to Novartis within 24 hours** of learning of its occurrence. The pregnancy should be followed up to determine outcome, including spontaneous or voluntary termination, details of the birth, and the presence or absence of any birth defects, congenital abnormalities, or maternal and/or newborn complications.

Pregnancy must be recorded on the Pharmacovigilance Pregnancy Form and reported by the investigator to the local Novartis Drug Safety and Epidemiology Department. Pregnancy follow-up should be recorded on the same form and should include an assessment of the possible relationship to the study treatment.

Any SAE experienced during the pregnancy and unrelated to the pregnancy must be reported on a SAE form.

The study drug must be discontinued, though the subject may stay in the study, if she wishes to do so. All assessments that are considered as a risk during pregnancy must not be performed. The subject may continue all other protocol assessments.

Pregnancy outcomes should be collected for the female partners of any males who took study treatment in this study. Consent to report information regarding these pregnancy outcomes should be obtained from the mother.

